## Research Protocol

### Title: Pair 2 Care: Peer Support for Caregivers of African Americans Living with Dementia

#### I. Objective

The purpose of this study is to test a peer support intervention for family caregivers who are caring for a loved one living with dementia. Peer Support for Caregivers of African Americans Living with Dementia (Pair 2 Care) is a co-created culturally sensitive family caregiver peer support intervention. We will determine if Pair 2 Care is feasible and acceptable by evaluating eligibility criteria, recruitment and retention data, protocol adherence, satisfaction, and feedback on appropriateness of the intervention for broader dissemination. At 6 months as compared to baseline, current family caregivers will report less anxiety and depression, higher quality of life, perceived social support, and self-efficacy for surrogate decision making as well as intent to use palliative care or hospice services as part of advance care planning and healthcare decision making for their care recipient living with dementia.

Throughout this protocol the terms 'caregivers' or 'family caregivers' will be used interchangeably to refer to family caregiver participants. Unless otherwise specified, both terms will be used to reference current and former family caregiver participants. Former family caregivers are 'mentors' and current family caregivers are 'mentees' and they referred to as such throughout this proposal. Study participants are current family caregivers (mentees) and former family caregivers (mentors). No professional, hired, formal caregivers such as nurses, physicians, and nursing assistants are included in the study. The terms Black and African American are also used interchangeably to represent Blacks residing in the US who are descendants of Sub-Saharan Africa.

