perceived benefits of peer support while caregiving and their willingness to serve as peer mentors to current family caregivers. Additional data from healthcare provider and community stakeholders support the need and potential benefits of peer support for ADRD caregivers. Based on these preliminary findings, there is an urgent need and exciting opportunity to address the unmet palliative care needs of current caregivers through peer support. For this innovative study, we will use the experiential expertise of former family caregivers as mentors to help current family caregivers as mentees with advance care planning and healthcare decision making. The purpose of this study is to test a peer support intervention for family caregivers who are caring for a loved one living with dementia. Peer Support for Caregivers of African Americans Living with Dementia (Pair 2 Care) is a co-created culturally sensitive caregiver peer support intervention. The following specific aims will be addressed:

[figure not shown]
**Aim 1:** Conduct feasibility and acceptability testing of Pair 2 Care in current ( $n=15$ ) and trained former ( $n=15$ ) African American ADRD family caregiver peers paired based on congruent identity traits (e.g., relationship to care recipient, gender identity, etc.). We will determine if Pair 2 Care is feasible and acceptable by evaluating eligibility criteria, recruitment and retention data, protocol adherence, satisfaction, and feedback on appropriateness of the intervention for broader dissemination.

**Aim 2:** Assess preliminary intervention outcomes of caregiver anxiety, depression, quality of life, social support, self-efficacy for surrogate decision making, and intent to use palliative care or hospice services to determine potential effectiveness of the Pair 2 Care Intervention. At 6 months as compared to baseline, current caregivers (mentees) will report less anxiety and depression, higher quality of life, perceived social support, and self-efficacy for surrogate decision making as well as intent to use palliative care or hospice services as part of advance care planning and healthcare decision making.

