**Table 3: Data Collection by Timepoints**

Participant	Timepoint		
		Baseline 0-Month	Intervention 3 & 6 Months
Mentee	
 
1. Demographics
 
2. Participant Intake Form
 
3. Anxiety (STAI-S)
 
4. Depression (CES-D)
 
5. Dementia stage* (QDRS)
 
6. Behavioral and psychological ADRD symptoms** (NPI-Q)
 
7. Quality of life (CGQOL)
 
8. Self-efficacy (SDM-SES)
 
9. Medical Outcomes Study Social Support Survey (MOS SSS)
 
10. Mentee Palliative and Hospice Care Intent Form
 
	
 
1. Anxiety
 
2. Depression
 
3. Behavioral and psychological ADRD symptoms*
 
4. Quality of life
 
5. Self-efficacy
 
6. Social support
 
	
 
1. Anxiety
 
2. Depression
 
3. Behavioral and psychological ADRD symptoms*
 
4. Quality of life
 
5. Self-efficacy
 
6. Social support
 
8. Satisfaction and Appropriateness Survey
 
9. Acceptability Survey
 
10. Mentee Palliative and Hospice Care Intent Form
 
11. Mentee Interview Guide
 

Mentor	
 
1. Demographics
 
2. Participant Intake Form
 
	
 
1. Mentor Interview Guide (month 6 or 7 only)
 
	

\*Instrument completed by current caregiver about care recipient

Feasibility and acceptability will be determined by evaluating eligibility criteria, recruitment, and retention data (e.g., consent, drop out, refusal rates), protocol adherence, satisfaction, and appropriateness of the intervention for broader dissemination. The Satisfaction and Appropriateness Survey (see appendix) will be used to rate current caregiver intervention satisfaction and appropriateness. The Acceptability Survey (see appendix) will be used to assess acceptability of Pair 2 Care. This information will be collected on the Study Feasibility Log (see appendix). Benchmarks will be assessed per Table 4.

[figure not shown]

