## K. Data Analysis

Descriptive statistics will be conducted on all participant demographic data using SPSS® or similar software.

Aim 1: Feasibility and acceptability of the Pair 2 Care Intervention in current ( $n=15$ ) and trained former ( $n=15$ ) African American ADRD family caregivers will be determined by our eligibility criteria, recruitment, and retention data (e.g., consent, drop out, refusal rates), protocol adherence, satisfaction, and appropriateness of the intervention for broader dissemination. We will conduct descriptive statistics for this Aim using proportion for categorical measures (recruitment, retention, and protocol adherence) and mean±standard deviation for continuous measures (80% satisfaction and 80% appropriateness). Interviews will be conducted with current caregivers to gather in-depth data on their Pair 2 Care Intervention experiences, including feedback on the likelihood of the intervention meeting the needs of African American ADRD caregivers. Interviews will be analyzed as described below. Aim 2: Descriptive statistics will be used to summarize sample characteristics and outcome measures (anxiety, depression, quality of life, social support, self-efficacy for surrogate decision making, and intent to use palliative care/hospice services) at each time point. For each outcome, we will use mixed-effects linear modeling for repeated measures to model the outcome as a linear function of fixed-effect of time. The model will also include subject-specific random intercepts to adjust for within-subject clustering from repeated measures. We hypothesize that at 6 months as compared to baseline, current caregivers will report less anxiety and depression, higher quality of life, higher social support, higher self-efficacy for surrogate decision making, and higher intent to use palliative care/hospice services. From the mixed-effects modeling, we will test this hypothesis by deriving contrast estimate of change of outcome between baseline and 6 months.

Power analysis suggested that our sample size ( $n=15$ ) will have only 38% power to detect a medium effect size of Cohen's  $d = 0.5$  for outcome change from baseline at 6 months. This effect size is equivalent to a clinical meaningful difference. Therefore, we will not rely on statistical significance. Instead, results interpretation will be guide by point estimates, precision of the estimates (e.g., 95% confidence interval), effect sizes, and their clinical significance.

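### Intent to use palliative or hospice care is to be tested at 6 months against baseline, but Table 3 does not schedule its form at 6 months

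*Combined protocol and SAP*

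**What the plan says.** Three places put intent to use palliative or hospice care under a 6-month hypothesis.

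- Section I (Objective) opens the hypothesis with "At 6 months as compared to baseline, current family caregivers will report less anxiety and depression" and includes intent among the outcomes that follow.
- Aim 2 in section II repeats the 6-month comparison and adds "as well as intent to use palliative care or hospice services as part of advance care planning and healthcare decision making".
- Section III.K (Data Analysis) restates it, ending the list of expected changes with "and higher intent to use palliative care/hospice services". It then says "we will test this hypothesis by deriving contrast estimate of change of outcome between baseline and 6 months".

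Section III.K also promises descriptive summaries of the outcomes, with the list ending "intent to use palliative care/hospice services) at each time point". The model for every outcome is a mixed model with random intercepts, described as one to "model the outcome as a linear function of fixed-effect of time".

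Table 3 in section III.G sets out which form is given when. For mentees, "10. Mentee Palliative and Hospice Care Intent Form" stands in the baseline list and again in the third list. It is absent from the list that belongs to "Intervention 3 & 6 Months". The instrumentation text in section III.G names the form but gives no time point. Section III.H gives the mentee survey times as baseline, 3 months, 6 months and the 1-month follow-up, without saying which forms are used at each.

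**The concern.** The analysis needs a 6-month intent value, and the data collection schedule does not provide one. Nothing else in the available documents adds it. A research team member working from Table 3 would complete the 6-month survey without the Intent Form, and a response missed at that visit cannot be recovered later.

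Section III.K says interpretation will rest on point estimates and their precision rather than on significance. An estimate that is missing, or interpolated without saying so, is therefore a real loss even in an underpowered pilot. Month 7 also answers a different question: pairing lasts 6 months, so Month 7 is one month after the planned peer support ends.

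**Working it through.** The plan gives no figure on this point to reproduce. The check compares the schedule with the analysis and then works out what the planned contrast would become.

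**Step 1: assign the three mentee lists in Table 3 to time points.** The heading of the third column is missing from the text available for this review, so the contents have to identify the lists.

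- List 1 has 10 items, including demographics and the intake form. It is baseline. The Intent Form is item 10.
- List 2 has 6 items, numbered 1 to 6 without a gap: anxiety, depression, behavioural and psychological symptoms, quality of life, self-efficacy, social support. It is 3 and 6 months. The Intent Form is not in it.
- List 3 has 10 entries, numbered 1 to 6 and 8 to 11. Item 10 is the Intent Form and item 11 the Mentee Interview Guide. Sections III.G and III.H place the mentee interview at the 1-month follow-up, which is Month 7.

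**Step 2: set schedule and analysis side by side.**

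| Mentee survey | Other five Aim 2 outcomes | Intent |
|---|---|---|
| Baseline | listed | listed |
| 3 months | listed | not listed |
| 6 months | listed | not listed |
| Month 7 | listed | listed |

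Intent is scheduled at 2 of 4 time points, and the 3 and 6 month list covers 5 of the 6 Aim 2 outcomes. With 15 mentees and complete data, that is 15 × 2 = 30 intent measurements, none at 6 months, against 15 × 4 = 60 if the form were used at every survey.

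**Step 3: what the contrast from baseline to 6 months becomes.**

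- *Time as categories.* The 6-month mean is a separate parameter with no data. The contrast cannot be estimated.
- *Time as a linear term.* With complete data at months 0 and 7 only, the fitted line passes through the two means, m0 and m7. The slope is (m7 − m0)/7, so the estimated change at 6 months is 6 × (m7 − m0)/7 = (6/7)(m7 − m0) = 0.857 (m7 − m0). This is interpolation, not a measured 6-month change. It assumes that the form gives a numeric score, as the planned linear model requires.

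**Step 4: can a Month 7 response count as the 6-month one?** Section III.G allows a 2-week window around each time point. On the widest reading, 14 days either side, two windows overlap only if their centres are less than 14 + 14 = 28 days apart. Months 6 and 7 are about 30 days apart, so they do not overlap.

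**The case against.** The strongest objection is that the evidence is a damaged table. Three mentee lists survive with only two time headings, list 3 skips item 7, and the mentor entry in the second list is marked for month 6 or 7 only. Assigning list 3 to Month 7 is therefore an inference, and that much stands. The rival reading, which shifts the headings one column to the right, fails: demographics would have no time point, the mentor interview would fall at baseline, and the mentee interview would fall at 3 and 6 months, against the text of section III.G. The numbering gap is in the list that already contains the Intent Form, not in the one that lacks it. The appendices and Figure 3 were not available, so Table 3 is the only schedule by form that could be checked.

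Second, the promise of summaries at every time point is weak support. The same sentence covers sample characteristics, and demographics are collected only at baseline, so it can be read as meaning wherever the item is measured. That is a fair reading. The finding rests on the 6-month contrast, which does not depend on that sentence.

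Third, the numerical effect under linear time may be small. Suppose the true change is 0.5 SD of the change scores, reached by month 6 and held at Month 7. Interpolation gives 0.5 × 6/7 = 0.43, an error of 0.07 SD. The half-width of a 95% confidence interval with 15 mentees is 2.145/√15 = 0.55 SD. The bias would be well inside the noise. This limits the harm under linear time, but it does nothing for categorical time, where no estimate exists.

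**Conclusion.** The inconsistency holds. Sections I, II (Aim 2) and III.K call for a change in intent from baseline to 6 months, and Table 3 as it reads supplies no 6-month value. If the table is followed, the contrast is either not estimable (categorical time) or equal to 6/7 of the change from baseline to Month 7 (linear time, complete data, numeric score). An oversight in the table is a likely explanation, but it would still misdirect data collection.

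The consequence is contained. It concerns one of six preliminary outcomes in a pilot with 15 mentees, no feasibility or acceptability benchmark in Table 4 depends on it, and the other five outcomes are unaffected. It should be fixed because the repair is small and the lost data could not be recovered. The conclusion assumes that list 3 is Month 7 and that no unseen appendix schedules the form at 6 months.

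**What to change.** Add the Mentee Palliative and Hospice Care Intent Form to the 6-month mentee survey in Table 3, and keep Month 7 as the follow-up value. Months 3 and 6 share a column, so mark the entry as 6 months only, or collect it at 3 months too if intent is meant to be summarised at every survey. If it is not collected at 3 months, state in section III.K the time points at which intent will be summarised.

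If 6-month responses can no longer be obtained, restate the intent hypothesis and contrast as baseline versus Month 7 in sections I, II (Aim 2) and III.K, and disclose the change in the report. The coding of time for the other outcomes need not change.

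The cost is one more form at a survey that already takes place, plus an IRB amendment. No extra contact is needed. The added burden on mentees could not be judged, because the form is in an appendix that was not available.

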**Table 4: Feasibility and Acceptability Benchmarks**

Feasibility Benchmarks	
Eligibility Criteria	Criteria allows for enrollment goal to be met
Enrollment	Enrollment of 100% of participants in Year 1
Retention	Retain at least 70% of current and former caregivers
Intervention Training	At least 90% former caregivers complete training
Protocol Adherence	At least 80% adherence and keep record of suggested changes per FamCAB
Acceptability Benchmarks	
Satisfaction Survey	At least 70% completion rate; 80% satisfaction rate; 80% appropriateness rate
Interviews	80% interview completion

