## J. Internal Validity

Threats to internal and external validity exist. For example, the study team will not be able to control additional external support that the current caregiver is receiving simultaneously that may impact study findings. The team will also not be able to control if the relationship between the peers is not conducive to peer support. However, participants will be instructed to contact the research team should any issues arise. In the conduct of pre- and post- tests are strategically timed based on prior studies with a goal to help avoid any desire of the participants to remain consistent in their responses. Data collection forms will be completed via telephone or video call (via Zoom®) with a research team member for consistency and to avoid missing data. Study participants may have participated in the prior FamCare Study. This relationship over the time with the PI and the study may impact their perception of the study. However, the benefits of their continued participation in this co-created community-based study outweighs this threat and will be acknowledged in the study results. Over the course of the study, participants may drop out. To mitigate this, the research team will maintain constant connection with them through frequent check-ins via phone call, text messages, and email for check-ins and data collection as outlined.

To ensure threats to internal and external validity in the qualitative portion of the study, several measures will be taken to help to ensure trustworthiness of findings. At least three independent coders to help to ensure validation of conclusions. Member checking with up to two participants in each category (current and former caregivers) will be conducted to verify if understanding of data rang true to them. Study team interview training will help to ensure regularity in the delivery process. All interviewers will also be trained in interview data collection procedures for consistency in this process to reduce variability of findings as a result. Data will be reported with sufficient descriptive data with the intent to ensure that data transferability is possible to applicable settings or groups.

For this pilot study, that is thus not fully powered, data obtained regarding feasibility and acceptability of the intervention will not be generalizable to the larger population. Therefore, data obtained will be used to inform the next step study to test effectiveness of the intervention.

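### Does the plan need to say which standard deviation its clinically meaningful d = 0.5 is measured in?

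*Combined protocol and SAP*

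**What the plan says.** Under Aim 2 in section K (Data Analysis), each outcome is summarised descriptively at every time point and then modelled with a random-intercept linear mixed model. The quantity of interest is the contrast between baseline and 6 months. The next paragraph says the 15 mentees "will have only 38% power to detect a medium effect size of" Cohen's d = 0.5 for that change, and then: "This effect size is equivalent to a clinical meaningful difference". Because power is low, the plan declines to rely on significance. "Instead, results interpretation will be guide by point estimates, precision of the estimates" comes next, with a 95% confidence interval as the example of precision, followed by effect sizes and their clinical significance.

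The plan names no SD for d. For the power figure it gives no alpha, sidedness, test, correlation or number assessed at 6 months. In the text supplied, no other number is tied to clinical meaning for an Aim 2 outcome; the instruments are in appendices that were not supplied. Table 4 sets benchmarks for feasibility and acceptability only, including: "Retain at least 70% of current and former caregivers".

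**The concern.** For a within-person change, d can be the mean change divided by the SD of the change, by the baseline SD, or by the residual SD of the mixed model. These differ whenever the correlation between the two visits departs from particular values, and the plan gives no correlation. Having set significance aside, it leaves d = 0.5 as the only number in the supplied text attached to clinical importance. The same observed change could then be called clinically meaningful on one scale and not on another, with the scale chosen after the data are seen.

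The power figure also looks odd. Reading d as a number of SDs of the change, the natural reading for a change outcome, does not return 38% with 15 mentees at a two-sided 0.05 level. Finally, section J (Internal Validity) says that "data obtained will be used to inform the next step study to test effectiveness of the intervention", so an unlabelled d might be carried into the planning of a later trial.

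**Working it through.** **Inputs.** From section K: n = 15, d = 0.5, stated power 38%, random-intercept model. From Table 4: 70% retention, and 0.70 × 15 = 10.5, so at least 11 mentees. Assumed, because the documents do not give them: alpha 0.05, two-sided unless noted, and a baseline-to-6-month correlation r of 0.3 to 0.7 with equal SDs at both visits.

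**1. Can 38% be reproduced, and does it identify the SD?** Power comes from the noncentral t distribution with noncentrality dz × √n and n − 1 degrees of freedom (df) unless noted, where dz is the change in SD-of-change units.

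| Reading of d = 0.5 | dz | Further assumption | Power |
|---|---|---|---|
| SD of change | 0.5 | n = 15 | 43.8% |
| SD of change | 0.5 | n = 13 assessed | 38.2% |
| Baseline SD | 0.5/√(2(1 − 0.4)) = 0.456 | n = 15, r = 0.4 | 37.7% |
| Residual SD | 0.5/√2 = 0.354 | n = 15, one-sided, 28 df | 37.9% |
| Residual SD | 0.354 | n = 15, two-sided, 14 df | 24.8% |

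Each standardiser can reach 38% under some unstated assumption. The figure neither identifies the SD nor is shown to be in error.

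**2. How far does the choice move the 0.5 mark?** In baseline-SD units, 0.5 SD of change is 0.5 × √(2(1 − r)): 0.592 at r = 0.3, 0.500 at r = 0.5 and 0.387 at r = 0.7. The largest shift from 0.5 is 0.5 − 0.387 = 0.113.

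**3. How does that compare with the precision?** Using completers only, the 95% half-width in SD-of-change units is t(0.975, n − 1)/√n.

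- n = 15: 2.145/3.873 = 0.554
- n = 11: 2.228/3.317 = 0.672

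Multiplying by √(2(1 − r)) puts it in baseline-SD units.

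| r | Shift | Half-width, n = 15 | Ratio | Half-width, n = 11 | Ratio |
|---|---|---|---|---|---|
| 0.3 | 0.092 | 0.655 | 0.14 | 0.795 | 0.12 |
| 0.5 | 0 | 0.554 | 0 | 0.672 | 0 |
| 0.7 | 0.113 | 0.429 | 0.26 | 0.520 | 0.22 |

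The residual-SD reading moves the mark further. In baseline-SD units it is 0.5 × √(1 − r), which is 0.418 at r = 0.3 and 0.274 at r = 0.7. The larger shift, 0.226, is still 0.226/0.429 = 0.53 of the half-width at n = 15.

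**4. What if a reader did treat 0.5 as a cut-off?** Bivariate normal studies were simulated with n = 11 or 15, a true change of 0.4 or 0.5 baseline SD, and r from 0.3 to 0.7. The SD-of-change and baseline-SD versions fell on opposite sides of 0.5 in about 12% to 23% of studies. At r = 0.5 the two definitions coincide in the population, yet they still disagreed in about 13%, which is sampling error in two SDs estimated from 11 to 15 people. Only r = 0.7 exceeded 20%. Two replicate studies using the same definition disagreed about 41% to 50% of the time. The true changes were also set at or near the cut-off, where disagreement is likeliest.

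**The case for a change.** The best case for a change is that wide intervals do not define the value they are read against. Once significance is set aside, the reference for clinical importance should be fixed in advance, and doing so costs two sentences, with no effect on sample size, data collection or model. If d = 0.5 on the SD-of-change scale were entered into a later two-arm design as though it were on the raw scale, that design would ask for 64 per arm (80% power, two-sided 0.05). The matching raw effect would need 46 per arm at r = 0.3 or 106 at r = 0.7.

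Part of this stands. The SD is not named, the inputs to the 38% are not given, and a label would help readers. The rest is weaker. Section K uses d = 0.5 to describe what the sample could detect; it does not say that an outcome passes or fails there. The wording attaches d to the change, which leans towards the SD of change without settling it. The sample-size contrast requires a planner to mistake one scale for the other. The plan already provides the raw contrast and descriptive statistics at each time point, and if these include SDs, as is usual, the planner can divide by the baseline SD directly. The sentence in section J follows a remark about feasibility and acceptability data and does not say that d will size the next trial. Lastly, the addition would leave the standardiser and every power input for the authors to fill in; it offers neither a better method nor a corrected figure.

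**Conclusion.** The omission is real, but it is a reporting detail that an analyst would ordinarily supply when tabulating effect sizes. Followed as written, the plan yields a baseline-to-6-month contrast, its 95% confidence interval, an effect size and descriptive summaries by visit, with no reliance on significance. These support sound conclusions for a 15-person pilot that declares its own low power.

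The choice between SD of change and baseline SD moves the reference by at most 0.113 baseline SD, or 0.26 of the 95% half-width at n = 15. The less natural residual-SD reading moves it by up to 0.226, or 0.53 of the half-width. With so few mentees, sampling error outweighs the labelling question. The 38% cannot be called wrong, since plausible unstated inputs return it, and the plan draws from it only that power is low, which is equally true at 44%.

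This rests on an assumed two-sided 0.05 level, r between 0.3 and 0.7 with equal SDs at the two visits, and completers-only intervals. It would need another look if the appendices made d = 0.5 a formal decision threshold; nothing in the supplied text does.
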